The Effect of Gastric Acid Suppression on Probiotic Colonization

Study Protocol

NCT03327051

August 28, 2018

The Effect of Gastric Acid Suppression on Probiotic Colonization

BACKGROUND

A major role of gastric acidity is the digestion of food products and the elimination of potentially pathogenic bacteria that enter the gastrointestinal tract. The use of pharmacologic agents that reduce gastric acid secretion (i.e., H₂ receptor antagonists and proton pump inhibitors) has consequently been shown to influence the composition of the intestinal microflora.¹⁻³ Probiotics contain living microorganisms that are consumed for its putative benefits on the intestinal microbiota and intestinal health. However, despite widespread use of probiotics and acid suppressing effects, the effect of gastric acid suppression on the survival and colonization of probiotics organisms is currently unclear. We hypothesize that pharmacology-mediated gastric acid suppression will increase the colonization potential of probiotics. We propose to test this hypothesis in a randomized double-blinded placebo-controlled trial among healthy controls who initiate probiotics.

[figure not shown]
METHODS

- Study design: Randomized double-blind placebo-controlled trial
- Population: 15 + 15 healthy controls
- Exclusion criteria: any gastrointestinal condition, soy or gluten sensitivity, allergy to proton pump inhibitors, any chronic medical condition other than hypertension or hyperlipidemia, pregnancy, consuming herbs or probiotics
- Interventions
 - PPI (omeprazole 20 mg/day) + VSL #3 (900 billion bacteria)
 - VSL #3 (900 billion bacteria)
- Primary outcome
 - Quantitation of bacterial strains found in VSL #3 (*S. thermophilus*, *B. breve*, *B. longum*, *B. infantis*, *L. acidophilus*, *L. plantarum*, *L. paracasei*, *L. delbrueckii* subsp. *bulgaricus*)
- Secondary outcomes
 - Characterization of microbiota
 - Metabolome
 - Safety (reported symptoms)

Study Visits

- Timeline
 - Week -2: Run-in with either PPI or nothing x 2 weeks
 - Week 0: Initiation of VSL #3 x 4 weeks
 - Diet/symptom survey, blood, and stool collection at weeks -2, 0, and 4

Interested participants will be contacted on the phone and screened by the clinical research coordinator (CRC). If interested and eligible, the participant will be sent a stool collection kit by mail and scheduled for the initial study visit (Week -2).

Week -2

- Undergo formal informed consent process
- Complete baseline questionnaire

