# The Effect of Gastric Acid Suppression on Probiotic Colonization

## Statistical Analysis Plan

NCT03327051

December 13, 2019

The relative percentage abundance was obtained by summing the levels of VSL#3 probiotic strains detected in the study samples. Statistical analysis was performed using GraphPad prizm. Two-way ANOVA with Bonferroni posttest was used for multi-variable analyses (within-group differences between week 0 and week 4). A p-value of <0.05 would be considered statistically significant.

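### The SAP tests change only within each arm: it names no between-arm test of the PPI hypothesis, and leaves the ANOVA's factors, scale and matching unstated

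*SAP*

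**What the plan says.** The SAP is a single paragraph. It defines the analysed quantity: "The relative percentage abundance was obtained by summing the levels of VSL#3 probiotic strains detected in the study samples". It then gives the method: "Two-way ANOVA with Bonferroni posttest was used for multi-variable analyses (within-group differences between week 0 and week 4". The software sentence, "Statistical analysis was performed using GraphPad prizm", lists no options, and the threshold is "A p-value of <0.05 would be considered statistically significant". The SAP does not state the two factors, the measurement scale, whether samples are matched by participant, the error term or the number of Bonferroni comparisons. It does not expressly tie the ANOVA to the summed percentage.

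The protocol has no statistical section to fill these gaps. Its Background states: "We hypothesize that pharmacology-mediated gastric acid suppression will increase the colonization potential of probiotics". Methods gives "Population: 15 + 15 healthy controls", and a primary outcome of "Quantitation of bacterial strains found in VSL #3" that lists eight strains. The Study Visits timeline has "Diet/symptom survey, blood, and stool collection at weeks -2, 0, and 4", so the week 0 and week 4 samples come from the same people.

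**The concern.** The hypothesis is about a difference between randomised arms, but the only comparisons specified are inside each arm. A reader is then left to set one arm's verdict beside the other's, and a result of significant with PPI but not without would be taken as evidence that PPI works. That is not a test of the difference.

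The undefined ANOVA adds a second problem. If it is group by time on raw percentages, one error term serves both arms, so each arm's test depends on the other arm's spread. Abundance cannot be negative, so an arm that rises more will plausibly also vary more. A real control-arm rise could then be missed because the PPI arm is noisy. If the fit is also unmatched, it ignores the pairing.

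**Working it through.** **What each test addresses.** Write C and P for the true change from week 0 to week 4 in the control and PPI arms. The post-tests address C = 0 and P = 0. The hypothesis is P > C. No pair of within-arm verdicts settles the sign of P − C.

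**Inputs.** From the documents: 15 per arm, paired samples at weeks 0 and 4, and a 0.05 threshold. Assumed, because the documents are silent: two-sided tests, Bonferroni over two arms (2.5% each), complete data, log-normal abundance with week-0 median 0.1%, log-SD 0.5 to 1.5, within-person correlation 0.5, a 5-fold control rise, and a PPI rise of 5-, 7.5- or 15-fold. Simulations used 40,000 trials per scenario. The plan has no power figure to reproduce.

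**Discordant verdicts with no PPI effect.** If both arms rise 5-fold and each is tested alone with power p, the chance that PPI is significant and control is not is p(1 − p).
- Log-SD 1.0, raw paired t, p about 0.83: 0.83 × 0.17 = 0.14.
- Log-SD 1.5, p about 0.32: 0.32 × 0.68 = 0.22.

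The mirror pattern is equally likely.

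**Concordant verdicts with a real PPI effect.** On logs at log-SD 1.0, within-arm power is about 100% for a 5-fold rise, and no lower for a larger rise with the same log spread. Both arms then come out significant whether PPI rises 5-fold or 15-fold, and the verdicts do not show a 15/5 = 3-fold difference.

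**Pooled error on raw percentages.** With r the ratio of PPI to control SD of change, pooling multiplies the control arm's standard error by √[(1 + r²)/2]. In the simulations r is 1.0, 1.5 and 3.1 at PPI rises of 5-, 7.5- and 15-fold, which gives factors of 1.0, √(3.25/2) = 1.27 and √(10.61/2) = 2.30. Control-arm power at log-SD 1.0:

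| PPI rise | Own-arm paired t (df 14) | Pooled repeated measures (df 28) | Unmatched ANOVA (df 56) | Cost of pooling | Further loss if unmatched |
|---|---|---|---|---|---|
| 15-fold | 84% | 15% | 13% | 69 | 2 |
| 7.5-fold | 83% | 54% | 49% | 29 | 5 |
| 5-fold | 84% | 77% | 71% | 7 | 6 |

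At log-SD 0.5, pooled power is about 75% at 15-fold and over 99% at 7.5-fold. At log-SD 1.5, pooled repeated-measures power is about 6%, 20% and 32% at 15-, 7.5- and 5-fold, against 32% own-arm.

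**Same mechanism, different model.** Take normal change scores and a control rise of 0.876 SD, which gives 80% own-arm power. Pooled power is then 84%, 76%, 40% and 9% at r = 1, 1.25, 2 and 3.

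**Change of scale.** With the same log-normal data analysed on logs, without zeros, pooled repeated-measures power is about 100% at log-SD 1.0 and 96% at log-SD 1.5 for all three PPI rises. The loss therefore comes from pooling on the raw scale, where spread grows with the mean.

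**Change of factors.** Strain by time, run separately in each arm, also fits the SAP's wording. Nothing is then pooled across arms, and the table does not apply.

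**The case against.** The strongest reply is that the damage from pooling is conditional throughout. It needs a group by time model, raw percentages and a more variable PPI arm, and the documents establish none of these. With equal spreads and normal changes, pooling even helps slightly (84% against 80%). If the control arm were the more variable one, the distortion would reverse. All of this stands, so the power figures illustrate a risk and do not describe what happened.

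Two stronger readings are tempting. The first is that pooling manufactures a false PPI effect, because PPI significant with control not occurs in 84-86% of simulated trials at a 15-fold PPI rise. But PPI truly works there, so the direction is right. With equal rises the pattern occurs in 19-22% of pooled analyses against 14% own-arm, an excess of 5-8 points. At log-SD 1.5 it is 21-25% against 22%, essentially no excess. The second is that the plan inflates type I error. Under normal changes the PPI arm's rate does reach about 7.4% against a nominal 2.5% at r = 2, but only if the arms differ in spread with no change in mean. Nothing in the documents suggests that.

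It can also be said that a group by time ANOVA produces an interaction term, which does compare the arms. But the SAP does not say the model is group by time, does not name the interaction, and describes its purpose as within-group differences. None of these replies supplies the missing between-arm test.

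**Conclusion.** The point holds in two parts of unequal strength. The firm part is that the SAP names no between-arm test for a between-arm hypothesis, and does not define its ANOVA well enough to be reproduced. This rests on the text alone. The 14-22% discordance rate that illustrates it assumes raw-scale paired tests and equal 5-fold rises.

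The conditional part is the loss of control-arm power: about 69, 29 and 7 points at log-SD 1.0, only if the ANOVA was group by time on untransformed sums. Only the repeated-measures comparison isolates pooling; the extra 2 to 6 points in an unmatched fit reflect ignored pairing. A reader might infer that the plan's ANOVA did hide a control-arm rise. The documents do not support that, because they give no scale, factors, variances, correlation or effect size. The change is worth making; confidence in the size of the effect is moderate at best.

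**What to change.** - **Primary test:** one between-arm comparison at week 4, an ANCOVA on log abundance adjusting for week 0, reported as a ratio with 95% CI. As sensitivity analyses, repeat it with a second zero offset and give a rank-sum test on change.
- **Secondary tests:** within-arm week 0 to week 4 change by Wilcoxon signed-rank on each arm's own participant-paired differences, Bonferroni-adjusted over the two arms. This needs no zero offset.
- **Reporting:** state the factors, scale and matching of the ANOVA that was run and keep its result. The SAP is written in the past tense, so label the re-analysis post hoc if data had been seen.

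The cost is SAP wording and a re-run on the planned samples, with three drawbacks.
- A post hoc analysis carries less weight.
- The ratio depends on the offset. With about half of week-0 values at zero (assumed), offsets of 0.001, 0.01 and 0.1 percentage points give 3.7, 3.25 and 2.6 for a true ratio of 3.0, with test size 4.3-5.2%.
- Power for modest effects is low. At log-SD 1.0 without zeros the ANCOVA has 91% power for 15- against 5-fold, but 23% for 7.5- against 5-fold. The rank-sum test has 85% and 19%.

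Week 0 also follows two weeks of PPI or placebo (Study Visits timeline). The adjusted ratio therefore describes differences arising after VSL#3 starts, and the report should say so.

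### An optional refinement, not an error: Holm's step-down could replace the Bonferroni post-test on the two within-arm contrasts at the same 5% family-wise level and with no loss of power

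*SAP*

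**What the plan says.** The SAP is a single paragraph. Its endpoint is one summed quantity: "The relative percentage abundance was obtained by summing the levels of VSL#3 probiotic strains detected in the study samples". The test is given as "Two-way ANOVA with Bonferroni posttest was used", and the contrasts are specified in brackets as "within-group differences between week 0 and week 4". The decision rule is "A p-value of <0.05 would be considered statistically significant". The number of comparisons in the family, sidedness, confidence intervals and a power target are not stated.

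The protocol's METHODS list gives the population as "15 + 15 healthy controls", without a sample-size calculation. It gives the primary outcome as "Quantitation of bacterial strains found in VSL #3", followed by eight named organisms. The BACKGROUND states the hypothesis that "pharmacology-mediated gastric acid suppression will increase the colonization potential of probiotics".

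**The concern.** Single-step Bonferroni holds every contrast in the family to the same reduced threshold, even after one of them has already been rejected. Holm relaxes the threshold for the contrasts that remain, and needs no extra assumption to do so. In a trial with 15 participants per arm, power that can be had without raising the family-wise error rate is worth having.

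The setting is also one where the difference could show. Both arms receive VSL #3, so a rise from week 0 to week 4 in both is plausible, and that is the case in which Holm gains. At stake is whether the second of two real rises is declared significant.

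**Working it through.** **Inputs.** From the SAP: alpha 0.05, Bonferroni, within-arm week 0 versus week 4 contrasts, one summed endpoint. From the protocol: two arms of 15. Derived: family size m = 2 arms × 1 endpoint = 2. Assumed, because the documents are silent: two-sided tests and the effect sizes below. The plan gives no power figure to reproduce.

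**Is Bonferroni valid here?** Each contrast is tested at 0.05/2 = 0.025. The bound is 0.025 + 0.025 = 0.05. For independent tests the family-wise error is 1 − 0.975² = 0.0494, against 1 − 0.95² = 0.0975 without correction. It is valid.

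**What Holm changes.** The smaller p-value is still tested at 0.025. If it is rejected, the larger is tested at 0.05 instead of 0.025. Nothing else differs.

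**Closed form for two independent tests, both effects real.** Let a be the unadjusted power of each test (at 0.05) and b its power at 0.025.
- At least one rejected, both methods: 1 − (1 − b)².
- Both rejected: b² with Bonferroni; a² − (a − b)² with Holm.
- Gain in average power per test: b(a − b).

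For a = 0.80 the non-centrality is 1.960 + 0.842 = 2.802. The critical value at 0.025 is 2.241, so b = Φ(2.802 − 2.241) = 0.712.
- At least one: 1 − 0.288² = 91.7%, identical for both methods.
- Both: 0.712² = 50.7% with Bonferroni; 0.64 − 0.088² = 63.2% with Holm.
- Average per test: 71.2% with Bonferroni; (91.7 + 63.2)/2 = 77.5% with Holm.

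| Unadjusted power | Average, Bonferroni | Average, Holm | Both, Bonferroni | Both, Holm |
|---|---|---|---|---|
| 50% | 38.9% | 43.2% | 15.1% | 23.8% |
| 80% | 71.2% | 77.5% | 50.7% | 63.2% |
| 90% | 84.1% | 89.1% | 70.8% | 80.7% |

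**Only one arm rises.** The gain for the real effect is (a − b) × 0.025 = 0.088 × 0.025 = 0.2 points (71.2% to 71.4%).

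**A model closer to the trial.** Simulation with 15 per arm, pooled error on 28 df, no dropout and 400,000 replicates; changes are in SD units of the within-person change.

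| Change in the two arms | Per contrast, Bonferroni / Holm | Both, Bonferroni / Holm | At least one, either method |
|---|---|---|---|
| 0.5, 0.5 | 35% / 39% | 13% / 21% | 56.3% |
| 0.8, 0.8 | 76% / 83% | 59% / 72% | 93.5% |
| 1.0, 1.0 | 93% / 96% | 86% / 92% | 99.2% |

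With unequal effects the gain goes mainly to the weaker arm. At 0.5 and 1.0, the weaker contrast moves from 35% to 45% and the stronger from 92.7% to 93.6%.

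**Error control in the same simulation.** With no effect in either arm, family-wise error is 0.049 for both methods. With an effect in one arm only, the false-positive rate in the other is about 0.025 with Bonferroni and 0.035 to 0.049 with Holm. Holm spends more of the error allowance but stays within 5%. In no replicate did Bonferroni reject a hypothesis that Holm retained.

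**The case against.** The strongest objection is that this is a preference and not a defect. Bonferroni is valid, and the same comment could be made about any plan that uses it. That stands, and it is why the point is graded as a refinement. Four stronger readings that a reader might infer are not supported.

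- *That Bonferroni buys nothing.* It gives simple simultaneous intervals that match its tests (critical t on 28 df 2.37, against 2.05 unadjusted). Holm has no equally simple counterpart. The SAP does not say that intervals will be reported, so the benefit is available but not used in the text.
- *That the loss is that of an eight-strain family.* The protocol names eight organisms, but the SAP sums them and sets out no strain-level tests. For eight independent tests at 80% unadjusted power, all effects real, average power would be 53% against 64%. That describes an analysis the SAP does not plan.
- *That the correction is what produces results significant in one arm only.* At 80% power with no correction at all, exactly one of two real rises is significant in 2 × 0.8 × 0.2 = 32% of trials. Bonferroni gives 91.7 − 50.7 = 41% and Holm 91.7 − 63.2 = 28.5%. Most of this discordance comes from testing each arm separately.
- *That Holm would bring the analysis closer to the trial's question.* The hypothesis concerns acid suppression against none. Greater power for each within-arm rise does not test that difference.

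A further objection concerns timing. The SAP is dated December 13, 2019 and is largely in the past tense, so the analysis may already have been run. Moving then to a rule that can only add rejections is a post-hoc change. This does not remove the improvement, but it means that the change must be disclosed.

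**Conclusion.** The point holds as a cheap improvement to the tests that the SAP states. That Holm controls the same family-wise 5% and is never less powerful is a theorem and depends on no effect size. The size of the gain does depend on assumptions that the documents do not settle: a family of two, two-sided tests, independence, and both rises real. At 80% unadjusted power it is about 6 points in average power and 12 to 13 points in the chance of detecting both rises. It is smaller at 50% and at 90%. There is no gain in the chance of any finding, and practically none if only one arm rises. The importance is low, and lower than that of the missing between-arm contrast.

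**What to change.** In the SAP, replace the Bonferroni post-test with: Holm step-down adjusted p-values, family = the two within-arm week 0 versus week 4 contrasts, significant if the adjusted p is below 0.05. This also states the family size, which the SAP leaves open.

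If any analysis has already been run, record the change with its date and reason, and show the Bonferroni results next to the Holm results.

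The cost is one phrase; no new data are needed. The downside is that simultaneous intervals matching the tests are less direct; Bonferroni or unadjusted 95% intervals can still be shown if labelled as such. If strains are later tested separately, that family needs its own definition. The between-arm contrast (group-by-time interaction) has to be specified separately, because this change does not provide it.

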- Provide pre-collected stool
- Blood collection
- Receive and initiate blinded drug (PPI or placebo); no observation required
- Receive stool collection kit

Week 0

- Complete follow-up questionnaire
- Provide pre-collected stool
- Blood collection
- Receive and initiate VSL #3; no observation required
- Receive stool collection kit

Week 4

- Complete final questionnaire
- Provide pre-collected stool
- Blood collection

Drug Sourcing

- VSL #3, omeprazole, and placebo to be purchased from compounding pharmacy

Financial Considerations:

Payment

Research participants will be compensated [REDACTED] at completion of the study to cover travel expenses. A gift card may be used for human subject reimbursement.

Specimen Storage and Processing

Specimens will be collected, processed, and stored in the -80° freezer in the [name] Laboratory. Microbiome and metabolome analyses will be performed at a core facility.

Data Storage

Paper records will be stored in a secure, locked cabinet at the Stanford Center for Clinical Research. Electronic clinical data will be stored on a REDCap database hosted on Stanford IT-managed servers.

REFERENCES

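### The only contrast the SAP names starts at week 0, after two weeks of randomised drug, so any PPI effect during the run-in is subtracted without being estimated, and the week -2 stool has no stated role

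*SAP*

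**What the plan says.** The Timeline under Study Visits in the protocol puts the randomised drug first: "Week -2: Run-in with either PPI or nothing x 2 weeks". The Week -2 visit list has participants "Receive and initiate blinded drug (PPI or placebo); no observation required". The probiotic comes two weeks later: "Week 0: Initiation of VSL #3 x 4 weeks". Sampling covers all three visits: "Diet/symptom survey, blood, and stool collection at weeks -2, 0, and 4". The size is given as "Population: 15 + 15 healthy controls".

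The SAP is one paragraph. Its endpoint is the summed relative abundance of the VSL #3 strains. Its method is "Two-way ANOVA with Bonferroni posttest was used for multi-variable analyses", and the only comparison it names is "within-group differences between week 0 and week 4". The threshold is "A p-value of <0.05 would be considered statistically significant". It does not mention week -2, a baseline covariate, a run-in comparison or a between-arm contrast, and it does not list the ANOVA factors or their levels.

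**The concern.** By week 0 the two arms have already been treated differently for two weeks. The protocol's Background itself says that acid-suppressing drugs alter the intestinal flora, so a run-in effect on this endpoint is plausible on the trial's own premises. The endpoint is a relative abundance. It can move because resident bacteria of the listed species change, or because other taxa change and shift the denominator, and either can happen before any VSL #3 is taken.

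A contrast that starts at week 0 takes such an effect out of the result. That may be what is wanted if the question is probiotic uptake, and not if the question is the whole effect of the PPI. The SAP does not say which effect it targets and plans no estimate of the part it removes, although the week -2 and week 0 samples would supply one. A reader given only the week 0 to 4 differences could not separate a PPI effect on resident bacteria from a PPI effect on the probiotic.

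**Working it through.** **No figure to reproduce.** The documents give no power, SD, correlation or effect size. Everything below except n = 15 per arm and the 0.05 level is an assumption. The SAP does not state sidedness; two-sided is assumed.

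**1. What the week 0 to 4 change estimates.** Let d be the PPI-minus-control difference at week 0 and T the same difference at week 4. Randomisation makes the expected difference at week -2 zero. Then:

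- arm difference in week 0 to 4 change = T - d
- arm difference at week 4 = T
- arm difference at week 0 = d

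This is algebra and needs no assumed value. Reading T - d as uptake does assume that the resident effect would have stayed at d until week 4. Both arms receive VSL #3, so the trial cannot test that.

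**2. An example (assumed values).** The PPI raises resident levels from 1.0% to 1.5% in the run-in, and VSL #3 adds 1.0 point in each arm.

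| | Week -2 | Week 0 | Week 4 | Change 0 to 4 |
|---|---|---|---|---|
| PPI | 1.0 | 1.5 | 2.5 | +1.0 |
| Control | 1.0 | 1.0 | 2.0 | +1.0 |
| Difference | 0 | 0.5 | 0.5 | 0 |

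The change gives zero, which is right for uptake. The week 4 level gives 0.5 point, which is right for the total PPI effect. Only the week 0 row entry explains why they differ, and no comparison of it is planned.

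**3. How far the two targets can part.** Take T = 1 SD and a week 0/week 4 correlation of 0.5, so that the change has variance 2(1 - 0.5) = 1 times that of a single visit. Two-sample t-test, 15 per arm:

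| d (SD) | T - d (SD) | Power for the change contrast |
|---|---|---|
| 0 | 1.0 | 75% |
| 0.2 | 0.8 | 56% |
| 0.5 | 0.5 | 26% |
| 0.8 | 0.2 | 8% |

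A run-in shift in the opposite direction (d below zero) would enlarge the contrast instead.

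**4. Precision at week 4.** With 15 per arm, 80% power and 28 degrees of freedom, the detectable difference without a covariate is 1.06 SD. Adjusting for week -2 multiplies it by sqrt(1 - r²), where r is the week -2/week 4 correlation (the one degree of freedom spent on the covariate is ignored):

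- r = 0.3: 1.06 × 0.954 = 1.01 SD
- r = 0.5: 1.06 × 0.866 = 0.92 SD
- r = 0.7: 1.06 × 0.714 = 0.76 SD

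A change from week 0 multiplies it by sqrt(2(1 - r)), where r is now the week 0/week 4 correlation: 1.25, 1.06 and 0.82 SD at 0.3, 0.5 and 0.7.

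The two correlations need not be equal. With 0.5 for week -2/week 4 and 0.8 for week 0/week 4, the relative variances are 1 - 0.25 = 0.75 for the adjusted week 4 comparison and 2(1 - 0.8) = 0.40 for the change. The change score is then the more precise of the two, though it estimates T - d and not T.

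**The case against.** The strongest reply is that week 0 is the right reference. The hypothesis concerns colonisation by the probiotic, VSL #3 starts at week 0, and week 0 is the last sample before it. In the example above, the week 0 to 4 change correctly reports no uptake effect, while a week 4 comparison would count 0.5 point of resident bacteria as colonisation. This stands. Removing d is an error only if the total PPI effect is the target, and neither document says that it is.

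Three stronger readings are tempting, and the documents do not support them.

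- *The SAP uses a contaminated baseline that conceals the run-in effect.* The SAP never calls week 0 a baseline. Week 0 is among the analysed visits, so an arm difference there can be recovered. What is missing is a plan to estimate it.
- *The week -2 stool was left out of the analysis.* The SAP text gives it no role, but the ANOVA's time levels are not listed, so its use cannot be excluded.
- *Ignoring week -2 costs precision.* That depends on correlations the documents do not give. People consuming probiotics are excluded, so week -2 levels may be low and may predict week 4 weakly. At r = 0.3 the gain is only from 1.06 to 1.01 SD.

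It is also fair to say that the absence of any named between-arm comparison is the larger gap at this place in the SAP, since the hypothesis and the randomised design call for one. The choice of reference visit is secondary to that, and one model can settle both.

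**Conclusion.** The point holds in a limited form. The one named contrast is within group and begins after two weeks of randomised drug. The only sample taken before that drug has no stated role, and any run-in effect on the endpoint is subtracted from the week 0 to 4 change and estimated nowhere. That much follows from the visit schedule and the SAP wording.

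Its size is unknown. The change contrast falls short of the week 4 effect by exactly d, and the documents give no d. In the illustration with T = 1 SD, a d between 0.2 and 0.8 SD leaves 0.8 to 0.2 SD. This does not make week 0 a wrong reference for uptake. It means that the target effect should be stated and the run-in effect reported. The precision gain is a possible extra: 1.06 SD down to between 1.01 and 0.76 SD over assumed correlations of 0.3 to 0.7.

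**What to change.** Replace the named contrast with one repeated-measures model of the weeks 0 and 4 abundance: arm, visit and arm-by-visit, with the week -2 value as covariate and its slope allowed to differ by visit. If abundance is log-transformed, state the rule for zeros, which are plausible before any probiotic is taken.

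Name one between-arm contrast as primary:

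- the week 0 to 4 change, if the target is probiotic uptake under established acid suppression; or
- week 4, if the target is the total PPI effect.

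Report the other, and the arm difference at week 0 (the run-in effect), as secondary. A single named primary contrast keeps the 0.05 test to one comparison. If the two-way ANOVA is kept, list its factors, time levels and repeated-measures structure, and say whether week -2 enters it.

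The cost is SAP wording and a re-run of the analysis; stool at all three visits is already in the protocol. The SAP is written in the past tense, so the analysis may already have been done. In that case the added contrasts should be labelled post hoc.

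The protocol describes the control run-in as nothing in the Timeline and as placebo in the Week -2 visit list. The two passages must be reconciled so that the week 0 comparison has a defined control.

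### The SAP's only stated output for the primary outcome is a p<0.05 verdict on within-group change; it specifies no PPI-versus-control estimate or 95% CI

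*SAP*

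**What the plan says.** The protocol (BACKGROUND) sets a directional hypothesis about the drug: "We hypothesize that pharmacology-mediated gastric acid suppression will increase the colonization potential of probiotics". METHODS gives the design as "Study design: Randomized double-blind placebo-controlled trial", the size as "Population: 15 + 15 healthy controls", and the primary outcome as "Quantitation of bacterial strains found in VSL #3", followed by eight named organisms. It states no time point, scale or effect measure for that outcome. Stool is collected at weeks -2, 0 and 4; the blinded drug starts at week -2 and VSL #3 at week 0.

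The SAP defines the analysed variable: "The relative percentage abundance was obtained by summing the levels of VSL#3 probiotic strains detected in the study samples". It then names the test and the only contrast: "Two-way ANOVA with Bonferroni posttest was used for multi-variable analyses (within-group differences between week 0 and week 4". It closes with the decision rule: "A p-value of <0.05 would be considered statistically significant".

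Neither document gives a between-arm contrast, an effect measure, a confidence interval, a target difference, an SD or a power. The only marked redaction is the participant payment, so this is not blacked-out text.

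**The concern.** Randomization protects one comparison, PPI against placebo. The SAP directs its significance rule at a different one, the change within each arm. Every participant takes VSL #3 from week 0, so a rise in VSL#3 strains by week 4 could occur in both arms whether or not acid suppression matters. A significant rise in one arm, or in both, therefore does not answer the hypothesis.

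The tempting shortcut is to read significance in the PPI arm and non-significance in the placebo arm as evidence for the drug. That pattern arises often by chance when the arms do not differ. With no between-arm estimate or interval planned, a reader would also have no stated way to see which sizes of PPI effect the 30 participants support and which they rule out.

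**Working it through.** There is no planned power or precision figure to reproduce; the sample size is stated without a derivation.

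**Inputs from the documents.** 15 per arm; threshold 0.05; Bonferroni posttest; within-group contrast of week 0 and week 4.

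**Assumptions, because the documents are silent.** Two-sided tests; all 15 per arm evaluable; Bonferroni over two tests (one per arm, so 0.025 each), with 0.05 unadjusted shown for comparison; a separate paired t-test in each arm on 14 df; log10 SDs of 0.3, 0.5 and 1.0 for the fold-change illustration.

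**1. What two within-arm verdicts say about the drug.** Let both arms have the same true change, 0.5 SD of the change, so the PPI effect is zero. The noncentrality is 0.5 × √15 = 1.94. The chance p that one arm is significant, and the chance 2p(1 − p) that exactly one of the two is:

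| Level per arm | p | 2p(1 − p) |
|---|---|---|
| 0.025 | 0.317 | 2 × 0.317 × 0.683 = 0.43 |
| 0.05 | 0.438 | 2 × 0.438 × 0.562 = 0.49 |

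The result depends on the common change. At 0.3, 0.7 and 0.9 SD the chance is 21%, 48% and 29% at the 0.025 level, and 31%, 41% and 18% at 0.05. Over these values, discordant verdicts occur in 18% to 49% of trials with no drug effect.

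**2. Precision of the contrast the SAP names.** The unadjusted 95% half-width for one arm's change is t(0.975, 14)/√15 = 2.145/3.873 = 0.55 SD of the change. This interval describes one arm and says nothing on its own about PPI against placebo.

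**3. Precision of the contrast the trial randomizes to test.** The unadjusted between-arm 95% half-width is t(0.975, 28) × √(2/15) = 2.048 × 0.365 = 0.75 SD of the quantity compared. With an assumed 13 or 12 evaluable per arm it is 0.81 or 0.85 SD. Two-sided power reaches 80% at a true difference of 1.06 SD and is 26% at 0.5 SD.

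**4. The same on a ratio scale**, if abundance were analysed as log10. The half-width as a factor is 10^(0.748 × SD); a two-fold effect is 0.301 on this scale.

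| Assumed log10 SD | CI factor either side | Power for a true two-fold effect |
|---|---|---|
| 0.3 | 10^0.224 = 1.7 | 76% |
| 0.5 | 10^0.374 = 2.4 | 36% |
| 1.0 | 10^0.748 = 5.6 | 13% |

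At SD 0.3 an estimate near 1 would exclude a two-fold change; at 0.5 or 1.0 it would not. Only the interval shows which case applies.

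**The case against.** The best defence is that silence is not refusal. The SAP does not say that estimates or intervals will be withheld, and a two-way ANOVA compares group means and can include a group-by-time term. That stands. A reader might infer that the trial cannot say how much acid suppression changes abundance. The documents do not support this: the randomized samples at weeks 0 and 4 allow a between-arm estimate and interval with no change in design. Nor does 15 per arm cause the omission; it only makes the interval wide. What remains is that the SAP names neither the between-arm term nor its estimate as the result.

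The protocol's hypothesis is also directional with no target size, so the plan does not contradict a stated aim to estimate. This is fair. The point rests on the missing randomized comparison more than on a missing interval, which alone would be a reporting detail.

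Two further inferences fail:

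- **A non-significant result would always be compatible with a several-fold rise.** This depends on the unknown SD and on the estimate. At a log10 SD of 0.3 and an estimate near 1, it is false.
- **Significant estimates from so small a trial would run high.** With a true 0.5 SD they average 0.94 SD. That comes from selecting on significance, and adding an interval does not cure it, so it does not support this change.

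Finally, the fold-change figures assume a log scale that the SAP does not mention. They illustrate precision and do not describe the planned analysis.

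**Conclusion.** The point holds in this form: the stated output for the primary outcome is a within-group p<0.05 verdict, and no PPI-versus-placebo estimate or 95% CI is specified. The plan as written therefore does not estimate the randomized effect. It does not follow that the trial is unable to.

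The consequence is material. Under equal true changes of 0.5 SD, the two within-arm verdicts disagree 43% of the time at 0.025 and 49% at 0.05. These figures assume independent paired tests on 15 per arm. The replacement comparison has an unadjusted half-width of about 0.75 SD with full follow-up. Any translation to fold changes rests on assumed SDs. The change should be made, but the omission does not invalidate the trial.

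**What to change.** Replace the SAP's last two sentences with text to this effect:

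> The primary result is the PPI minus placebo difference in summed VSL#3 abundance at week 4, adjusted for the week 0 value (or the between-arm difference in week 0 to week 4 change), with its 95% confidence interval; the two-sided p-value is given alongside. If a log scale is used, the result is a ratio of geometric means, with a stated rule for undetected strains. Within-arm changes are descriptive and are shown with confidence intervals. A result with p≥0.05 is reported as inconclusive unless the interval excludes a named difference.

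The SAP should choose one of the two forms. Both are between-arm comparisons that use the pre-probiotic sample. However, week 0 follows two weeks of blinded drug, so they target the same quantity only if the run-in leaves the arms alike at week 0. The week -2 sample is the only one taken before the drug.

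The SAP is dated December 13, 2019 and describes the analysis in the past tense. If results are already known, the estimate and interval can still be reported, but the choice of contrast and any named difference should be labelled post hoc.

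The cost is SAP wording and one reanalysis of samples that the protocol already collects. The small downside is that a wide interval will show how imprecise the trial is.
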